3.8 Justification for interventions

The initial starting dose of ferrous sulfate (325 mg po tid) was chosen because this is currently the standard of care as outlined in the KDIGO guidelines for iron deficient individuals with CKD.

The starting dose of ferric citrate needed to balance the requirement to provide sufficient lowering of dietary phosphorus absorption to effect a decrease in FGF23 concentrations (and

thereby help attenuate the rise in hepcidin) while at the same time providing sufficient iron supplementation to treat iron deficiency anemia. While a starting dose of 1 gram of ferric citrate three times a day was considered, in the seminal study comparing the efficacy of ferric citrate vs. placebo in pre-dialysis CKD patients,²⁰ the average final dose of ferric citrate needed to achieve adequate phosphorus reduction was 5.1 grams per day. Therefore, we chose 2 grams three times per day with meals to provide sufficient phosphorus binding effect to lower FGF23 while at the same time providing adequate iron supplementation to compare against ferrous sulfate.

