3.9 Procedures and Evaluations

3.9.1 Assessment of Safety

3.9.1.1 Risks and Discomforts

Phlebotomy

Subjects will experience the usual discomfort caused by phlebotomy. The total amount of blood to be collected for the entire study period will be ~150 ml, or ~ ½ cup, less than the volume of blood collected during a single blood donation (500 ml or 2 cups). We will exclude subjects with hemoglobin levels < 7 g/dl for women and < 8 g/dl for men during their screening visit.

Severe hypophosphatemia

Ferrous citrate is an oral phosphorus binder. It is possible that participants taking the prescribed ferrous citrate dose (2 grams three times a day with meals) may develop low serum phosphorus concentrations. In a prior study of 72 individuals with moderate CKD not requiring dialysis being treated with a higher cumulative dose of ferric citrate (5.1 grams/day) than proposed in the current study, there were no events of symptomatic hypophosphatemia, and only two instances of serum phosphorus concentrations falling below 2.5 mg/dL (which resolved on their own). Therefore, the likelihood of severe hypophosphatemia occurring is low, particularly since we will exclude individuals with serum phosphorus concentrations less than 3.0 mg/dL on screening labs. Nonetheless, serum phosphorus concentrations will be monitored through the study. Study drug titration will occur as follows:

- If serum phosphorus concentrations fall to between 2.5 and 3.0 mg/dL, participants will be asked to reduce the dose of ferric citrate to 1 tablet three times a day with meals.
- If serum phosphorus concentrations fall below 2.5 mg/dL, participants will be asked to hold the study drug until serum phosphorus concentrations are above 3.0 mg/dL, and then re-start the study medication at 1 tablet three times a day with meals.
- If serum phosphorus concentrations remain below 3.0 mg/dL despite reduction in study drug dose, the participant will be asked to stop ferric citrate and follow-up blood draws will be obtained two weeks after to ensure that the phosphorus concentration recover to above 3.0 mg/dL.

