4.3 Statistical Plan

To compare the baseline characteristics between the two groups, student's t-test or chi square test will be used for parametric and non-parametric variables respectively. Subjects' baseline values will serve as the reference for comparison with changes post-intervention. Longitudinal changes in the primary outcome variables will be examined using repeated measures linear mixed models. In these models, time and treatment group will be the fixed variables and participants will be modeled as random terms. We will first test for a time by treatment group interaction to determine whether the change in the outcome variables over time differs by treatment group assignment. If we detect a statistically significant interaction, we will stratify the analysis by treatment group and test the main effect of time in stratified models. If we do not detect a significant interaction, we will remove the interaction term from the model and will test for the main effects of time and treatment group. If we find any differences in baseline characteristics despite randomization, we will adjust for these covariates in secondary models. We will analyze data using an intention-to-treat principle such that all randomized participants who received at least one dose of study medication and had at least one post-baseline assessment will be included to assess efficacy.

4.4 Sample Size Calculation:

The sample size estimation is powered to detect a significant difference in the change in ferritin in response to oral ferric citrate vs ferrous sulfate challenge. In a prior study, treatment with ferric citrate for 12 weeks raised serum ferritin by 77.5 [95%CI 56.2-98.7] as compared to placebo. To detect as small as a 20% lower rise in ferritin in individuals taking ferrous sulfate vs. ferric citrate over a similar period of intervention, we would need recruit 60 individuals overall (30 per arm) assuming a type I error of 0.05 and a power of 80%. This will also provide ample power to detect at least a 20% difference in the change in TSAT as well. While we also plan on examining changes in hepcidin in this protocol, we did not specifically power the analysis for this outcome variable as it is a secondary outcome.

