A prior randomized, controlled study of patients with stage 3-5 CKD (eGFR 10-59 ml/min/1.73m²) showed that treatment with oral ferrous sulfate (325 mg po bid) resulted in a mean increase in hemoglobin of 0.2 ± 0.9 g/dL (Agarwal R et al, Am J Nephrol 26:445-454, 2006). If we assume that treatment with ferric citrate for 12 weeks will increase hemoglobin by 0.6 ± 0.4 mg/dL (Block et al, Am J Kidney Dis 65(5):728-736), the current sample size of 60 participants overall will provide ~60% power to detect a mean difference in hemoglobin increase of 0.4 ± 0.7 between the two groups.

References

3. Ganz T. Heparin, a key regulator of iron metabolism and mediator of anemia of inflammation. Blood 2003;102:783-8.
10. Nemeth E. Anti-heparin therapy for iron-restricted anemias. Blood 2013;122:2929-31.

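### The stated 80% power for a 20% smaller ferritin rise needs an SD of about 21 ng/mL, which the quoted confidence interval does not support; 30 per arm gives roughly 12–25%

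*Combined protocol and SAP*

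**What the plan says.** Section 4.4 bases the sample size on the between-arm difference in ferritin change. Its source is a prior study in which "treatment with ferric citrate for 12 weeks raised serum ferritin by 77.5 [95%CI 56.2-98.7] as compared to placebo". The target is a 20% lower rise on ferrous sulfate, for which "we would need recruit 60 individuals overall (30 per arm) assuming a type I error of 0.05 and a power of 80"%. The section gives no SD, no sidedness, no dropout allowance and no reference number for the prior study. On the other primary outcome it adds only: "This will also provide ample power to detect at least a 20% difference in the change in TSAT as well".

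Two other places bear on the size of the prior study. Section 3.9.1.1 refers to safety experience "In a prior study of 72 individuals with moderate CKD not requiring dialysis being treated with a higher cumulative dose of ferric citrate", at 5.1 g/day. Section 3.8, citing reference 20 for a comparison of ferric citrate with placebo in pre-dialysis CKD, says that "the average final dose of ferric citrate needed to achieve adequate phosphorus reduction was 5.1 grams per day". The title of reference 20 describes a 12-week placebo-controlled trial, which matches the 12 weeks in section 4.4.

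The closing paragraph of section 4.4 reports hemoglobin power with its inputs shown: the trial "will provide ~60% power to detect a mean difference in hemoglobin increase of 0.4 ± 0.7 between the two groups".

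**The concern.** A 20% reduction in a rise of 77.5 is small beside the uncertainty of the estimate itself: the target is 15.5 and the CI half-width is 21.25. A trial of 30 per arm can resolve 15.5 only if patients vary little in their ferritin change, and the section never says how much they vary. The closeness of 21.25 to the SD that 30 per arm would need suggests that the precision of a mean difference was read as the spread between patients.

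Ferritin is one of the two primary outcomes (section 4.1) and the only one behind the choice of 60. If the power is far below 80%, a non-significant result could be read as evidence against a 20% difference that the trial had little chance of detecting. If the true difference is near 15.5, a significant result in that direction would overstate it, because only a much larger observed difference can reach significance at this size. The second point does not apply if the true difference is as large as the design can detect.

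**Working it through.** **Inputs.** From section 4.4: difference 77.5, 95% CI 56.2 to 98.7, 20% target, alpha 0.05, power 80%, 30 per arm. From section 3.9.1.1: 72 patients on ferric citrate. The ferritin unit (ng/mL) is taken from the eligibility criteria. The size of the prior placebo arm is not given, so a range is assumed.

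**Sidedness.** Section 4.4 does not state it. The hemoglobin calculation (0.4 with SD 0.7, 30 per arm) gives 58.6% two-sided by noncentral t (60.0% by normal approximation) and 70.6% one-sided. The protocol says about 60%, so two-sided is used below and one-sided is shown as a check.

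**Reproducing the planned size.**

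- Target: 0.20 × 77.5 = 15.5
- CI half-width: (98.7 − 56.2)/2 = 21.25
- Entering 21.25 as the SD: n per arm = 2 × (2.80 × 21.25/15.5)² = 29.5, which rounds to the stated 30. By t-test, power is 79.3% at 30 per arm and 80.7% at 31.

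**SD that the claim needs.** Solving the t-test power for 80% at 30 per arm gives SD = 21.07 (23.86 one-sided).

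**What the CI implies.** The standard error of the prior difference is 21.25/1.96 = 10.84. With prior arms m₁ and m₂, SD = 10.84/√(1/m₁ + 1/m₂).

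- For equal arms, an SD of 21.07 needs m = 2 × (21.07/10.84)² = 7.6 per arm (9.7 with the one-sided SD).
- With 72 on ferric citrate, an SD of 21.07 needs a placebo arm of about 4.0 (5.2 one-sided).

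**Power of the planned size for 15.5 ng/mL** (single-time-point t-test, 30 per arm):

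| Assumed prior arms | SD | Power, two-sided | Power, one-sided | Difference with 80% power | As % of 77.5 | Smallest significant observed difference | n per arm for 80% |
|---|---|---|---|---|---|---|---|
| 36 + 36 | 46.0 | 25.0% | 36.1% | 33.8 | 44% | 23.8 | 140 |
| 72 + 72 | 65.1 | 14.8% | 23.2% | 47.9 | 62% | 33.6 | 278 |
| 100 + 100 | 76.7 | 12.0% | 19.2% | 56.4 | 73% | 39.6 | 385 |

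The last five columns follow from the SD; all but the one-sided power are two-sided. The difference with 80% power is 0.736 × SD. Unequal prior arms stay in the same range: 72 treated with 24 on placebo gives SD 46.0, and 72 with 144 gives 75.1.

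**Allowance for repeated visits.** Averaging three post-baseline visits multiplies the SD by √((1 + 2ρ)/3), where ρ is the within-patient correlation. Fully independent visits (ρ = 0), with the whole 15.5 present at each, give 60.4%, 34.9% and 26.6% for the three rows. At an assumed ρ of 0.5 the figures are about 35%, 20% and 16%.

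**Allowance for covariate adjustment.** To bring the SD down to 21.07, adjustment would have to remove 1 − (21.07/46.0)² = 79% of the variance in the first row and 1 − (21.07/76.7)² = 92% in the last. Section 4.3 plans adjustment only in secondary models.

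**The case against.** The strongest reply is that the 12–25% needs a figure the protocol does not give. Section 4.4 names no reference for the CI. The 72 patients come from a safety paragraph that does not mention placebo, and are tied to the placebo-controlled study by the shared 5.1 g/day. That paragraph is not carefully worded: it calls 5.1 g/day higher than this trial's dose, although 2 g three times a day is 6 g/day, and those statements need reconciling. If 72 were the total and split 48 to 24, power would be 27.5%, slightly outside the range. This stands as a limit on the precision of the range. It does not rescue the claim, because an SD near 21 fits the CI only for a prior trial of about 8 patients per arm.

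A second reply is that section 4.3 plans a repeated-measures mixed model with a time-by-treatment interaction, not a t-test at one time point. That also stands: the power figures and the 24–40 ng/mL significance threshold are approximations, and a CI taken from an adjusted model could shift the back-calculated SD. But even fully independent visits leave power at about 60% for equal prior arms of 36 (about 65% for a 48/24 split), and realistic correlation leaves far less.

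Third, the half-width explanation is an inference. The hemoglobin paragraph uses values treated as true SDs, so the half-width was not used throughout. The shortfall does not depend on how the 30 was reached.

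Finally, the TSAT sentence is unsupported but has not been shown to be wrong.

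**Conclusion.** The concern holds. The 80% power claimed for a 15.5 ng/mL difference is not supported by the CI on which it is built. For prior arms of 36 to 100 each, two-sided power at 30 per arm is about 12–25%; if both prior arms were near 72, it is about 15%. A one-sided test gives at most 36% over the same range. The stated target would need roughly 140 to 385 per arm, while the design as it stands has 80% power for differences of about 34 to 56 ng/mL, a 44% to 73% lower rise.

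These figures assume that the 72 patients belong to the study that gave the CI, that the CI is an unadjusted two-sample interval with a common SD, and that a single-time-point comparison is a fair proxy for the planned model. They also assume no dropout. Section 3.7.2 says that withdrawals after randomization will not be replaced, so losses would lower power further. No variation of these assumptions that was examined brings power to 80%. Because the statement justifies the trial's size on a primary outcome, it must be corrected.

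**What to change.** Keep 60 patients and rewrite section 4.4:

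1. Take the SD of the ferritin change from the cited study, either as reported or from its standard error and actual arm sizes. Print the SD and the reference, and state that the test is two-sided.
2. Restate the power for a 15.5 ng/mL difference at 30 per arm, and the difference detectable with 80% power.
3. Give the reason for keeping 60 against that detectable difference, for example the 2-year recruitment period mentioned in section 3.3.
4. Support the TSAT statement with a calculation that shows its SD, or delete it.

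The cost is wording in one section, with no extra patients and no change to conduct or analysis. The stated power will be much less favourable, as the hemoglobin paragraph already accepts for its own outcome.
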